Appendix 9 SF-36v2TM

15 March 2022, page 192/216

SF-36v2® Health Survey © 1992, 1996, 2000, 2010 Medical Outcomes Trust and QualityMetric Incorporated.

All Rights Reserved.

[figure not shown]
SF-36® is a registered trademark of Medical Outcomes Trust. (SF-36v2® Health Survey Standard, United States (English))

EudraCT 2016-004719-10 EDMS-ERI-207656619

Confidential

[figure not shown]
15 March 2022, page 193/216

EudraCT 2016-004719-10 EDMS-ERI-207656619

[figure not shown]
Confidential

Version 615 March 2022, page 194/216

Confidential

[figure not shown]
15 March 2022, page 195/216

[figure not shown]
Confidential

EudraCT 2016-004719-10 EDMS-ERI-207656619

15 March 2022, page 196/216

[figure not shown]
EudraCT 2016-004719-10 EDMS-ERI-207656619

EudraCT 2016-004719-10 EDMS-ERI-207656619

Confidential

[figure not shown]
15 March 2022, page 199/216

EudraCT 2016-004719-10 EDMS-ERI-207656619

Confidential

[figure not shown]
Version 615 March 2022, page 200/216

EudraCT 2016-004719-10 EDMS-ERI-207656619

Confidential

15 March 2022, page 201/216

EudraCT 2016-004719-10 EDMS-ERI-207656619

Confidential

15 March 2022, page 202/216

15 March 2022, page 203/216

EudraCT 2016-004719-10 EDMS-ERI-207656619

Confidential

Appendix 10 Relapse assessment questionnaire

TO BE FILLED OUT BY THE TREATING NEUROLOGIST AND/OR STUDY NURSE

When applicable, for each of the Questions 1 to 5 below, complete either the phone			
interview or visit interview questions.			
Phone interview	Visit interview During a visit at the study site (scheduled or unscheduled)		
 Subject calling the site to report new/worsened symptoms 			
 Scheduled call from the site to the subject for relapse detection 			
Date of phone interview	Date of visit		
dd mmm yy dd mmm yy			
1. Is / was the subject having new neurological symptom(s) or an acute worsening of pre-existing neurological symptom(s)?			
~	Visit		
□ Yes → Go to Question 2	☐ Yes → Go to Question 2		
□ No → STOP Relapse investigation	□ No → STOP Relapse investigation		
2. Are / were symptoms suggestive of a relapse (e.g. rapid onset, typically hours or days as opposed to weeks/months, symptom type)?			
~	Visit		
☐ Yes/possibly → Go to Question 3	\square Yes/possibly \rightarrow Go to Question 3		
 □ Definitely not → STOP Relapse investigation and enter subject's symptoms or diagnosis on the eCRF AE page 	 □ Definitely not → STOP Relapse investigation and enter subject's symptoms or diagnosis on the AE eCRF page 		

15 March 2022, page 204/216

3. Did the symptoms last >24 hours?			
2	Visit		
□ Yes/possibly → Go to Question 5 and complete date and time of start of symptoms	Yes/possibly → Go to Question 5 and complete date and time of start of symptoms		
□ No → Go to Question 4 and complete date and time of start of symptoms	□ No → Go to Question 4 and complete date and time of start of symptoms		
Date of start of symptoms · · dd mmm yy	Date of start of symptoms ·		
Time of start of symptoms · hh mm	Time of start of symptoms hh mm		
4. Have the symptoms started within the last 24 hours? (To be answered only if answer to question 3 was "No")			
2	Visit		
☐ Yes → Go to Question 5	\square Yes \rightarrow Go to Question 5		
□ No → STOP Relapse investigation and enter subject's symptoms or diagnosis on the AE eCRF page	□ No → STOP Relapse investigation and enter subject's symptoms or diagnosis on the AE eCRF page		

15 March 2022, page 205/216

Confidential

5. Does / did the subject have concomitant fever or an infection and, if yes,
are/were the symptoms more likely due to fever/infection than to a
relanse?

relapse?			
~	Visit		
□ Yes→ STOP Relapse investigation and enter subject's symptoms or diagnosis on the AE eCRF page	□ Yes → STOP Relapse investigation and enter subject's symptoms or diagnosis on the AE eCRF page		
 No / not sure → Invite the subject to an unscheduled visit as soon as possible but at least 24 hours after the onset of symptom(s). → Go to Question 7 but if answer to question 4 was "Yes", answer additionally question 6 at the visit performed at least 24 hours after symptom onset 	 No / not sure → If this visit occurs 24 hours from symptom onset, invite the subject to an unscheduled visit as soon as possible but at least 24 hours after the onset of symptom(s) → Go to Question 7, but if question answer to question 4 was "Yes", answer additionally question 6 at the visit performed at least 24 hours after symptom onset 		

Question 6 - 8 can only be asked during a visit at the study site (scheduled or unscheduled) which occurs at least 24 hours after the symptoms onset.

Visit interview

during a visit at the study site (scheduled or unscheduled)

Date of visit

(complete only if different from the one reported for question 1 to 5)

dd mmm yy

6. Did the symptoms last >24 hours?

(To be answered only at a visit performed at least 24 hours after onset of symptoms and if answer to question 4 was "Yes" during an earlier interview (i.e. an interview conducted within 24 hours from symptom onset)):

- □ Yes / possibly → Go to Question 7
- □ Definitely not → STOP Relapse investigation and enter subject's symptoms or diagnosis on the AE eCRF page

15 March 2022, page 206/216

EudraCT 2016-004719-10 EDMS-ERI-207656619

Confidential

7. Prior to the onset of this event, were the MS symptom(s) stable or improving over the last 30 days?

- □ Yes / possibly → Go to Question 8
- □ No → Choose 1 below option
 - □ The previous symptoms corresponded to a relapse, which is recorded in the eCRF
 - → STOP the relapse investigation for the new episode and enter the symptoms on the AE eCRF page unless the current symptoms are considered as part of the most recent relapse. Note: New or recurrent symptoms that occur less than 30 days following onset of a protocoldefined relapse should be considered part of the same relapse.
 - ☐ The previous symptoms were not due to a relapse
 - ightarrow Go to Question 8 and make sure that those previous symptoms are recorded on the AE eCRF page

8. Is there another and better explanation for the subject's current symptoms than an MS relapse?

- □ Yes → STOP Relapse investigation and enter subject's symptoms or diagnosis on the AE page
- \square No \rightarrow Enter symptoms in the "Relapse symptom form".
 - → The subject should undergo EDSS assessment by the efficacy assessor within 7 days from the relapse onset (Note: no referral is needed at scheduled visits where EDSS/FS score is assessed as part of the scheduled assessment for this visit in this event, the EDSS assessment planned for this visit will be used as part of the relapse assessment)

15 March 2022, page 207/216

EudraCT 2016-004719-10 EDMS-ERI-207656619

Confidential

Appendix 11 Relapse symptom form

TO BE FILLED OUT BY THE TREATING NEUROLOGIST

Relapse symptom Form				
Visual (op	tic) functions			
	bject report any new or worsening symptoms to the visual functions?	☐ Yes If yes, complete the below	0	No
	Decreased vision			
	Changed vision (excl. double vision) e.g. blurre	d vision		
	Decreased visual field			
	Scotoma			
	Ocular pain			
-	Other If other, please specify:			
Brainstem	functions			
	bject report any new or worsening symptoms to the brain stem functions?	☐ Yes If yes, complete the below		No
	Double vision			
	Sudden hearing decrease or loss			
	Oscillopsia			
	Numbness in the face			
	Symptoms of facial nerve weakness (e.g. proble closure, facial asymmetry)	ems with eye or	mouth	
	Dysarthria			
	Dysphagia			
	Vertigo			
	Other If other, please specify:			

EudraCT 2016-004719-10 EDMS-ERI-207656619

15 March 2022, page 208/216	

Pyramidal	functions				
Did the subject report any new or worsening symptoms belonging to the pyramidal functions?		☐ Yes If yes, complete the below	□ No		
	Muscle stiffness/spasticity				
	Impaired walking or hopping				
	Other If other, please specify:				
Cerebella	rfunctions				
	bject report any new or worsening symptoms to the cerebellar functions?	☐ Yes If yes, complete the below	□ No		
	□ Difficulties keeping balance while sitting, standing or walking				
	Tremor				
	Vertigo				
	Clumsy movements				
٥					
Sensory functions					
Did the subject report any new or worsening symptoms belonging to the sensory functions?		☐ Yes If yes, complete the below	□ No		
	Any abnormal sensation				
	Tingling				
	Central pain syndrome				
0	Other If other, please specify:				

15 March 2022, page 209/216

EudraCT 2016-004719-10 EDMS-ERI-207656619

Bowel and Bladder functions				
Did the subject report any new or worsening symptoms belonging to the bowel and bladder functions?		☐ Yes If yes, complete the below	□ No	
	 Urinary retention 			
	□ Urinary urgency			
	 Urinary incontinence 			
	 Constipation 			
	Bowel incontinence			
	Other If other, please specify:			
Cerebral f	unctions			
Did the subject report any new or worsening symptoms belonging to the Cerebral functions?		☐ Yes If yes, complete the below	□ No	
□ Problems with cognition (e.g. memory, concentration)				
	Fatigue			
	Mood disorders			
	Other If other, please specify:			

• If yes, please specify:

15 March 2022, page 210/216

EudraCT 2016-004719-10 EDMS-ERI-207656619

Ambulatio	on		
Did the subject report any new or worsening symptoms belonging to the ambulation?		☐ Yes If yes, complete the below	□ No
	□ Reduced walking distance		
	 Need for increased/new assistance (e.g. from no assistance to unilateral assistance) 		
	Reduced walking speed		
٥	Other If other, please specify:		
Other nev	v or worsening symptoms attributed to relapse bu systems	it difficult to clas	sify into
Did the subject report any other symptoms attributable to a relapse?			

15 March 2022, page 211/216

EudraCT 2016-004719-10 EDMS-ERI-207656619

Confidential

Appendix 12 Guidance on study conduct during the COVID-19 (coronavirus) pandemic

It is recognized that the Coronavirus Disease 2019 (COVID-19) pandemic may have an impact on the conduct of this clinical study due to, for example, self-isolation/quarantine by participants and study-site personnel; travel restrictions/limited access to public places, including hospitals; study site personnel being reassigned to critical tasks.

In alignment with recent health authority guidance, the sponsor is providing options for study-related participant management in the event of disruption to the conduct of the study. This guidance does not supersede any local or government requirements or the clinical judgment of the investigator to protect the health and well-being of participants and site staff. If at any time a participant's safety is considered to be at risk, study intervention will be discontinued, and study follow-up will be conducted.

Scheduled visits that cannot be conducted in person at the study site will be performed to the extent possible remotely/virtually or delayed until such time that on-site visits can be resumed. At each contact, participants will be interviewed to collect safety data. Key efficacy endpoint assessments should be performed if required and as feasible. Participants will also be questioned regarding general health status to fulfill any physical examination requirement.

Every effort should be made to adhere to protocol-specified assessments for participants on study intervention, including follow up. Modifications to protocol-required assessments may be permitted via COVID-19 Appendix after consultation with the participant, investigator, and the sponsor. Missed assessments/visits will be captured in the clinical trial management / EDC system for protocol deviations. Discontinuations of study interventions and withdrawal from the study should be documented with the prefix "COVID-19-related" in the case report form (CRF).

The sponsor will continue to monitor the conduct and progress of the clinical study, and any changes will be communicated to the sites and to the health authorities according to local guidance. If a participant has tested positive for COVID-19, the investigator should contact the sponsor's responsible medical officer to discuss plans for study intervention and follow-up. Modifications made to the study conduct as a result of the COVID-19 pandemic should be summarized in the clinical study report.

GUIDANCE SPECIFIC TO THIS PROTOCOL:

• Patient Visits & Assessments

Assessments that may be completed over the phone include assessment of relapse, eC-SSRS, review of adverse events and concomitant medications. Vital signs can be collected in a remote

15 March 2022, page 212/216

Confidential

EudraCT 2016-004719-10 EDMS-ERI-207656619

setting by the subject, caregiver, delegated site staff/in-home nurse, or general practitioner, as feasible. Please ensure the remote method you choose is allowable per local regulations and fully documented in the subject source files.

It is important for safety monitoring of laboratory parameters to continue according to the protocol schedule. If access to the study site (and therefore the central lab) is not possible, local laboratories may be used to monitor laboratory parameters. An alternative, if allowed per local regulations, is to use delegated site staff/in-home nursing to collect blood samples at the subject's home and ship to either the central laboratory or an accredited local laboratory for testing. Where local laboratories are used, it's important to ensure appropriate documentation of laboratory reference ranges. If abnormal laboratory values requiring follow-up in the protocol, or any other abnormality deemed critical by the investigator, are unable to be followed-up, it is recommended to temporarily interrupt (for a maximum of 12 weeks) until the abnormality can be considered resolved or permanently discontinue study treatment.

Other protocol-required examinations and assessments not conducive to remote administration can be conducted as soon as it is feasible for the subject to come to the site for a visit. As clinically indicated, other local resources such as the subject's general practitioner or delegated site staff/inhome nursing can be considered.

• Study Drug Dispensation

If a subject is unable to travel to the site for a scheduled visit where study drug would be dispensed, the following alternate measures should be discussed with the sponsor and may be considered to ensure continuity of treatment:

- A caregiver or family member may pick up study drug on behalf of the subject if first discussed and agreed by the subject. The conversation with the subject must be documented in the source files. The subject must name the individual who will pick up study drug on their behalf. This is necessary for site staff to confirm the study drug is provided to the appropriate individual, ensure proper chain of custody of study drug, and to maintain subject privacy. This must be confirmed and documented in the subject source file.
- Investigative site staff may deliver study drug directly to the subject's home. The chain of custody and transit conditions must be clearly documented within the subject source file.
- If no other alternative is feasible, direct-to-patient shipment of study drug from the site may be considered with prior approval from the sponsor and relevant health authority, as applicable.
- It is important to remind subjects that in case of treatment interruption of 4 or more consecutive days, they should inform the investigator and/or site staff immediately. Ponesimod treatment can only be restarted with uptitration and on-site cardiac monitoring, as applicable, as described in the protocol.

15 March 2022, page 213/216

EudraCT 2016-004719-10 EDMS-ERI-207656619

Confidential

• COVID-19 Infection in MS Patients:

There is currently no available data suggesting that patients treated with ponesimod should have treatment interrupted during the COVID-19 pandemic. In general, patients receiving immunomodulators should continue treatment and continue to exercise precautionary measures to minimize the risk of infection. If a subject develops symptoms associated with coronavirus infection, it is recommended to confirm the diagnosis using locally approved laboratory kits and reported to the local health authorities, as required. Subjects with positive test results for coronavirus should have this recorded as an AE, and if hospitalized, this should be reported as an SAE. It is important to notify the treating physician of the subject's participation in this clinical study and details of the study treatment. It is also recommended to follow local MS Society recommendations.

• On-site Monitoring Visits:

In case on-site monitoring visits are not possible, your monitor may arrange remote site monitoring activities with you until the point at which regular on-site monitoring visits may resume.

All of the above measures are recommended for consideration on a temporary basis during the COVID-19 pandemic to enable continuity of treatment and to ensure that subject assessments, particularly those assessing relapse and safety, continue as outlined in the protocol without imposing health risk to subjects, their families, and site staff. Every effort should be made to complete all protocol-required assessments. Investigators should use their clinical judgment and benefit risk assessment in determining if a subject can continue study treatment in the absence of on-site clinic visits. If remote visits are not possible, or if in the investigator's judgment, appropriate safety monitoring is not feasible in a remote setting, the investigator should consider temporarily interrupting study treatment (for a maximum of 12 weeks per protocol) or discontinuing study treatment and initiating treatment with another available disease modifying treatment (DMT).

STUDY CONDUCT RELATED TO COVID-19 VACCINE DEPLOYMENT FOR NONCOVID-19 CLINICAL TRIALS

Current guidelines from global MS societies recommended that people with MS should be vaccinated against COVID-19. 1,2,3 Having MS does not increase the risk of COVID-19 virus infection or the risk to develop severe forms of the infection more than the general population and it is important that DMT in MS patients is continued and maintained. 4 It is therefore recommended that people with MS currently taking a DMT, including ponesimod, continue with their treatment unless advised to stop by their treating physicians (e.g., MS patients on DMT with risk factors for severe COVID-19 infections).

No clinical data are available on the efficacy and safety of vaccinations in patients taking ponesimod.

15 March 2022, page 214/216

EudraCT 2016-004719-10 EDMS-ERI-207656619

Confidential

Based on preclinical data, vaccinations may be less effective if administered during treatment.

There are 4 main types of COVID-19 vaccines (all non-live) that are currently available (see below). For a complete overview of the COVID-19 vaccine landscape, please refer to the WHO website.⁵

- **mRNA vaccines** are based on the SARS-CoV-2 spike glycoprotein antigen encoded by RNA and formulated in lipid nanoparticles;
- **Protein subunit vaccines** based on full-length spike protein (S), receptor-binding domain (RBD), non-RBD S protein fragments, and non-S structural proteins;
- **Vector vaccines** consisting of a recombinant adenovirus carrying the gene for SARS-CoV-2 virus spike glycoprotein;
- **Inactivated vaccines** use viruses whose genetic material has been destroyed so they cannot replicate, but can still trigger an immune response.

As stated in Section 5.2.2, vaccination with non-live vaccines is allowed while on study treatment if the vaccination is advised by the primary investigator / treating neurologist, based on her/his clinical assessment of the risk/benefit for the individual patient, and if supported by guidelines for vaccination relevant to this patient population, as applicable.

Therefore, all above mentioned COVID-19 vaccines may be administered to study subjects.

Important notes and reminders:

- Vaccination with live vaccines is prohibited, except if performed during a temporary treatment interruption period. In this case it must be performed not earlier than 1 week after the last dose of study treatment, and treatment can be reinitiated only after at least 4 weeks from completion of vaccination (see Section 5.2.3).
- Please report any administered vaccines on a Concomitant Medication page in the CRF.

If a patient is eligible for COVID-19 vaccination in accordance with their local regulations their participation in the study should be modified as required.

The reporting of any AEs (including SARS-CoV-2 infection or those associated with COVID-19 vaccination) should be reported as described in Section 10.

References:

- 1. MS International Federation 2021. MS, the coronavirus and vaccines updated global advice. Available from: https://www.msif.org/news/2020/02/10/the-coronavirus-and-ms-what-you-need-to-know/ews today 2021. Accessed 19 July 2021.
- 2. National MS Society 2021. COVID-19 vaccine guidance for people living with MS. https://www.nationalmssociety.org/coronavirus-covid-19-information/multiple-sclerosis-and-coronavirus/covid-19-vaccine-guidance#section-1. Accessed 19 July 2021.

EudraCT 2016-004719-10 EDMS-ERI-207656619

Confidential

15 March 2022, page 215/216

- 3. National MS Society 2021. MS treatment guidelines during coronavirus. Available from: https://www.nationalmssociety.org/coronavirus-covid-19-information/multiple-sclerosis-and-coronavirus/ms-treatment-guidelines-during-coronavirus. Accessed 19 July 2021.

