5.1.12.6 Liver abnormalities

15 March 2022, page 79/216

In the event of abnormal liver tests or signs and symptoms suggestive of drug-induced liver injury (DILI), the subject will be closely observed, liver tests will be repeated, and study treatment discontinuation should be considered according to the guidance provided in Table 5.

Note: All events of ALT or AST $\ge 3x$ ULN and total bilirubin $\ge 2x$ ULN ($\ge 35\%$ direct bilirubin) or ALT or AST $\ge 3x$ ULN and INR ≥ 1.5 may indicate severe liver injury (possible 'Hy's Law') and must be reported to sponsor in an expedited manner and as an SAE if SAE criteria are met. The INR stated threshold value will not apply to participants receiving anticoagulants.

15 March 2022, page 80/216

Confidential

Table 5 Guidance for subject monitoring and discontinuation for liver enzyme abnormalities

Item	Laboratory parameter	Guidance
1	ALT or AST ≥3 × ULN *	Start close observation. Repeat labs within 72 hours. See items 1a and 1b. * if ALT or AST ≥8 × ULN OR ALT or AST ≥3 × ULN and TBL ≥2 × ULN or INR >1.5a OR ALT or AST ≥3 × ULN with the appearance of fatigue, nausea, vomiting, right upper quadrant pain or tenderness, fever, rash, and/or eosinophilia (>5%) and retest cannot be done within 72 hours, permanently discontinue study treatment, and perform FU
1a	If at repeated labs, ALT or AST ≥3 × ULN < 8 × ULN	Continue close observation. Repeat labs twice weekly. See items 2a and 2b.
1b	If at repeated labs, ALT or AST <3 × ULN	Resume regular labs schedule.
2a	If at repeated labs, ALT or AST \geq 5 × ULN for >2 weeks	Permanently discontinue study treatment, and perform FU.
2b	If at repeated labs, ALT or AST ≥3 × ULN <5 × ULN for >2 weeks	Continue close observation. Repeat labs once or twice weekly.
3	 If at repeated labs: ALT or AST ≥8 × ULN ALT or AST ≥3 × ULN and TBL ≥2 × ULN or INR >1.5 a ALT or AST ≥3 × ULN with the appearance of fatigue, nausea, vomiting, right upper quadrant pain or tenderness, fever, rash, and/or eosinophilia (>5%) 	Permanently discontinue study treatment, and perform FU.

ALT = alanine aminotransferase; AST = aspartate aminotransferase; FU = follow-up; INR = International Normalized Ratio; TBL = total bilirubin; ULN = upper limit of normal range.

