a Note: All events of ALT or AST ≥3xULN and total bilirubin ≥2xULN (>35% direct bilirubin) or ALT or AST ≥3xULN and INR >1.5 may indicate severe liver injury (possible 'Hy's Law') and must be reported to sponsor in an expedited manner and as an SAE if SAE criteria are met. The INR stated threshold value will not apply to participants receiving anticoagulants.

15 March 2022, page 81/216

Confidential

EudraCT 2016-004719-10 EDMS-ERI-207656619

Whenever AST or ALT $\geq 3 \times 10^{-5}$ the upper limit of normal range (ULN) are recorded by the central laboratory, an alert will be sent to the principal investigator and the sponsor. The sponsor will contact the principal investigator to ensure that she/he will immediately contact the subject, and ask the subject about any potential symptoms. The subject will be closely observed and will be asked to return to the site as soon as possible after the time of receipt of the alert to repeat the liver enzyme and bilirubin tests by the central laboratory (unless the clinical situation mandates immediate local testing) according to the scheme illustrated in Table 5. Further diagnostic work-up (including hepatitis serological testing by the central lab) and consultation with a hepatologist or other specialist should be considered, and adequate medical management should be provided according to local practice and the clinical situation. Any clinically relevant finding meeting the definition of an AE will be recorded accordingly in the eCRF.

In the event of study treatment interruption, the subject will be closely observed and FU liver tests will be performed. Following study treatment interruption, if liver tests normalize and drug-related hepatotoxicity is unlikely, study treatment may be re-initiated at the discretion of the investigator. The decision to permanently discontinue study treatment will be made after evaluation of all available information concerning concomitant medications, other potential causes of hepatotoxicity, and the clinical status of the subject. NB: The re-initiation is not permitted for situations where the study treatment should be permanently discontinued according to Table 5. In all cases of permanent study treatment discontinuation, FU monitoring must be provided until signs and symptoms have resolved and changes in liver function are no longer regarded as clinically relevant or until medically indicated.

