The sponsor is providing options for study related participant management in the event of disruption to the conduct of the study. This guidance does not supersede any local or government requirements or the clinical judgement of the investigator to protect the health and well-being of participants and site staff. In case it is not possible to obtain initial informed consent of potential participant or updated written informed consent of study participant due to movement restrictions, study participant may provide consent verbally in the presence of an impartial witness. If, at any time, a participant's travel to the study site is considered to be dangerous, study participation may be interrupted, and study follow-up conducted. If it becomes necessary to discontinue participation in the study, the procedures outlined in the protocol for discontinuing study intervention will be followed.

If, as a result of the regional crisis scheduled visits cannot be conducted in person at the study site, they will be performed to the extent possible remotely/virtually or delayed until such time that on-site visits can be resumed. At each contact, participants will be interviewed to collect safety data. Key efficacy endpoint assessments should be performed if required and as feasible. Participants will also be questioned regarding general health status to fulfill any physical examination requirement.

Every effort should be made to adhere to protocol-specified assessments for participants on study intervention, including follow-up. Modifications to protocol-required assessments may be permitted after consultation with the participant, investigator, and the sponsor. All protocol deviations related to the regional crisis should be documented with the prefix "Regional Crisis" in the CRF. Missed/remote assessments/visits will be captured in the clinical trial management system for protocol deviations. Discontinuations of study interventions and withdrawal from the study should be documented with the prefix "Regional Crisis" in the CRF.

The sponsor will continue to monitor the conduct and progress of the clinical study, and any changes will be communicated to the sites and to the health authorities according to local guidance. Modifications made to the study conduct as a result of the regional crisis should be summarized in the clinical study report.

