It is important for safety monitoring of laboratory parameters to continue according to the protocol schedule. If access to the study site (and therefore the central laboratory) is not possible, local laboratories may be used to monitor laboratory parameters. An alternative, if allowed per local regulations, is to use delegated site staff/in-home nursing to collect blood samples at the patient's home and ship to either the central laboratory or an accredited local laboratory for testing. Where local laboratories are used, it is important to ensure appropriate documentation of laboratory reference ranges. If abnormal laboratory values requiring follow-up in the protocol, or any other abnormality deemed critical by the investigator, are unable to be followed up, it is recommended to temporarily interrupt (for a maximum of 12 weeks) until the abnormality can be considered resolved or permanently discontinue study treatment.

At times when courier support is not available to move samples to the central laboratory, then laboratory assessments should focus on the following order of priority:

- 1. Utilize local laboratory assessments required to ensure participant safety. Generally, this includes CBC (complete blood count) and serum chemistry assessments, as per protocol assessment schedule and investigator clinical judgement.
- 2. All samples such as biopsy tissue which have long-term stability should continue to be collected and stored at the study site. Other labs considered investigational, such as immunogenicity samples, can be collected and stored as per the protocol until a time where transportation services are restored.

3. Should local laboratories be used, please refer to the study protocol on what is to be collected in terms of local laboratory documentation, ie, laboratory ranges.

Study Drug Dispensation and Other Trial Supplies

Study drug supply is monitored via IWRS. It is imperative for ongoing management, any study medications dispensed is recorded in IWRS. Any interruptions of patient treatment due to supply availability, should be alerted to the Site Manager. Damaged supplies should be reported as soon as possible so managing re-supply can be prioritized. Trial related supplies such as laboratory kits may be interrupted. Local laboratory supplies may be utilized as outlined in the Study Laboratory Manual. For other supplies, consult with the Site Manager to discuss feasible options.

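### The Appendix 12 laboratory guidance offers a temporary interruption in liver cases where Table 5 requires permanent discontinuation

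*Protocol*

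**What the plan says.** **Appendix 12 (COVID-19), Patient Visits & Assessments.** The laboratory sentence covers abnormal values for which the protocol requires follow-up, and any other abnormality the investigator regards as critical, when follow-up is impossible. In that event "it is recommended to temporarily interrupt (for a maximum of 12 weeks) until the abnormality can be considered resolved or permanently discontinue study treatment". No parameter is excepted and Table 5 is not mentioned.

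**Section 5.1.12.6, Table 5 item 1.** ALT or AST of at least 3 × ULN calls for a repeat within 72 hours. A starred note lists three graver patterns and ends: "retest cannot be done within 72 hours, permanently discontinue study treatment, and perform FU". The text after the table adds: "The re-initiation is not permitted for situations where the study treatment should be permanently discontinued according to Table 5".

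**Regional-crisis guidance, Specific Laboratory Instructions.** This text follows the last page-numbered protocol page, so its standing is unclear. It repeats the sentence for values that are "unable to be followed up, it is recommended to temporarily interrupt (for a maximum of 12 weeks" and likewise has no liver exception.

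**The concern.** Both texts address the same event, an abnormal liver test that cannot be rechecked in time, and they allow different actions. Table 5 leaves one course, a permanent stop. Appendix 12 puts an interruption of up to 12 weeks beside it as an alternative and ties the interruption to resolution, which implies a restart.

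A site working from the guidance during a disruption could therefore keep a subject with a starred liver pattern on hold with restart in view, where the main protocol has closed that route. The liver is a live risk for this drug. Section 1.3.2.4 gives increased ALT as the most common treatment-emergent event on ponesimod in the core study (19.5%), and Appendix 4 lists severe liver injury as an event of special interest. The 19.5% covers all reports of increased ALT. It is not the frequency of the starred patterns, which the protocol does not give.

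**Working it through.** The check compares texts; no statistical figure is involved.

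**1. Is the situation the same?** Yes. Item 1 requires a repeat test, so a missed repeat is follow-up required by the protocol that could not be done. That is the trigger of the Appendix 12 sentence.

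**2. Which actions does each text allow?**

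| | Table 5 item 1, starred note | Appendix 12 laboratory sentence |
|---|---|---|
| ALT/AST ≥8 × ULN | permanent stop | interrupt up to 12 weeks, or permanent stop |
| ALT/AST ≥3 × ULN with bilirubin ≥2 × ULN or INR >1.5 | permanent stop | same two options |
| ALT/AST ≥3 × ULN with listed symptoms or eosinophilia >5% | permanent stop | same two options |
| Restart | barred (Section 5.1.12.6) | implied by interruption until resolution |

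**3. Does the ambiguity in the starred note matter?** The 72-hour condition can be read in two ways.
- It attaches to all patterns: the missed retest is the trigger for 3 of 3.
- It attaches only to the last: the missed retest is the trigger for 1, and the other 3 − 1 = 2 require a permanent stop at once.

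On either reading, once no retest is possible, interruption is not permitted for any of the three.

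**4. How far does the conflict reach?** Table 5 has items 1, 1a, 1b, 2a, 2b and 3, six in all. Items 1a to 3 act on repeat results, so only item 1 contains a missed-retest rule: 1 of 6. An isolated ALT/AST of at least 3 but below 8 × ULN without the added features has no immediate permanent-stop rule, so interruption does not conflict there. The lymphocyte rule in Section 5.1.12.2 needs a confirmed count below 0.2 × 10⁹/L, so interruption pending a repeat does not conflict there either. The 12 weeks agree with the general limit in Section 5.1.8; the dispute is over the permitted action, not the duration.

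**5. How many sentences lack the exception?** One in Appendix 12 (page 212/216) plus one in the regional-crisis text: 1 + 1 = 2.

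**6. Does the guidance say that Table 5 prevails?** No. Appendix 12 states "This guidance does not supersede any local or government requirements or the clinical judgment of the investigator". The protocol's own stopping rules are not on that list.

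**The case against.** The strongest reply is that the appendix relaxes nothing.

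- Its general text lets assessments be modified after consultation and says nothing of discontinuation criteria. The laboratory sentence is only a recommendation, and Section 13.5 binds the investigator to the approved protocol.
- The sentence already names permanent discontinuation, so it can be read as whichever action the protocol requires.
- Dosing stops at once on either branch, and restart is barred by Section 5.1.12.6. Any re-initiation after four or more missed days also needs a Day 1 visit and an IRT call (Section 8.5.3).
- Appendix 12 has a general stopping sentence: "If at any time a participant's safety is considered to be at risk, study intervention will be discontinued, and study follow-up will be conducted". The regional-crisis text says that, where participation has to be discontinued, "the procedures outlined in the protocol for discontinuing study intervention will be followed".
- The sponsor would usually know. Transaminase values of at least 3 × ULN that "are recorded by the central laboratory, an alert will be sent to the principal investigator and the sponsor", and possible Hy's Law events must be reported to the sponsor in an expedited manner whichever laboratory measured them.
- The trigger is remote: local laboratories and home sampling must have failed, and a starred pattern must be present.

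Most of this stands as to likelihood. A site can satisfy both texts by stopping permanently, the bar on re-initiation is unrestricted, and harm is unlikely.

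It does not remove the conflict. The permission to modify concerns assessments. The re-initiation visit concerns titration, cardiac monitoring and dispensing. Expedited reporting does not decide treatment. The safety-at-risk sentence depends on judgment where Table 5 sets thresholds. The automatic alert depends on central-laboratory results and is weakest when local laboratories stand in. Reading the sentence as whichever action the protocol requires adds words it does not contain.

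**Conclusion.** The concern holds. The Appendix 12 laboratory sentence states, without qualification, an option that Section 5.1.12.6 forbids for the starred patterns in Table 5 item 1. This is a contradiction within the document, not a detail left for elsewhere.

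Its practical weight is small: one of six Table 5 items, a rare coincidence of events, and several partial safeguards. No endpoint and no count of events of special interest changes. It is still worth correcting, because the rule concerned is a mandatory liver stop that covers possible Hy's Law cases, and the guidance is the text a site would consult when retesting has failed.

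The conclusion does not depend on how the 72-hour clause is read. That few subjects would be affected is a judgment, since the protocol gives no count. The Appendix 12 sentence is sufficient for the finding even if the regional-crisis text has no formal standing.

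**What to change.** Add one clause to the laboratory sentence in Appendix 12 and to the matching sentence in the regional-crisis guidance:

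> except where Table 5 requires permanent discontinuation, which applies unchanged and after which re-initiation is not permitted (Section 5.1.12.6)

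Leave Table 5 as it is, and keep the interruption option for all other abnormal values.

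The cost is one clause in each of two sentences, with no added visits, tests or eCRF changes. Section 13.6 requires a written amendment submitted to ethics committees and authorities, so the change should be carried in the next amendment and does not merit one of its own.
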